1.2. Secondary, exploratory objectives

- 1.2.1. To evaluate the safety of convalescent plasma (CP) administration in hospitalized COVID-19 patients
- 1.2.2. To evaluate viral shedding of SARSCoV-2 in nasopharyngeal or nasal samples before and on days 3, 7, and 14 after CP transfusion
- 1.2.3. To perform genomic analysis of the SARS-CoV-2 from patients before and after treatment with CP transfusion
- 1.2.4. Determine cumulative incidence of disease severity (transfer to ICU, type of respiratory support, LOS, and mortality)

2. Background

Passive antibody treatment involves the administration of antibodies against a specific infection to a susceptible individual to treat or ameliorate the severity of the disease caused by the infectious agent. Plasma from patients that have recovered from the infection is harvested and administered to the non-immune. The use of this modality of treatment dates back to the 1890's, but its popularity decreased during the antibiotic era.(Casadevall, 2020)

During the current SARSCoV-2 pandemic, with its associated high mortality and morbidity and the lack of demonstrated and effective treatment or vaccine, the induction of immunity with the transfusion of convalescent plasma offers a therapeutic alternative.

Convalescent plasma was studied during the SARS epidemic in 80 patients in Hong Kong.(Cheng 2005) Those treated before day 14 had improved prognosis defined by discharge from hospital before day 22, consistent with the notion that earlier administration is more likely to be effective. There is also anecdotal information on the use of convalescent serum in seriously ill individuals. Three patients with SARS in Taiwan were treated with 500 mL convalescent serum, resulting in a reduction in serum virus titer, and each survived (Yeh 2005)

PROTOCOL TITLE: Open, non-comparative pilot study to provide access to treatment with investigational convalescent plasma and measure antibody levels in patients hospitalized with COVID-19

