3. Contraindication to transfusion or history of prior severe allergic reactions to transfused blood products
4. On ECMO or in refractory shock at entry

5. Number of Subjects

This pilot aims to explore safety and measure antibody levels in patients treated with CP. We aim to enroll 30 subjects to ensure the estimate of *neutralizing antibodies* to be within 20% margin of error.

PROTOCOL TITLE: Open, non-comparative pilot study to provide access to treatment with investigational convalescent plasma and measure antibody levels in patients hospitalized with COVID-19

6. Study Timelines

Hospitalized patients will be enrolled as soon as their COVID-19 diagnosis is confirmed, using approved diagnostic methods, and will be followed until hospital discharge or death. Patient enrollment will start immediately after IRB approval. We anticipate a 3-month enrollment. The study will continue for another 24-months after the last enrollment during which we will be able to process and analyze data, and disseminate findings.

7. Study Endpoints

7.1. Primary endpoint:

- 7.1.1. Titers of SARS-CoV-2 neutralizing antibodies measured by focus reduction neutralization test (FRNT) at days 0 (pre-transfusion), 1, 3, 7 and 14 days of CP transfusion.

- 7.1.2. Availability of convalescent plasma

7.2. Secondary endpoints:

Clinical outcomes:

- 7.2.1 Serious adverse events
- 7.2.2 SARCoV-2 viral shedding in nasopharyngeal samples determined by RT-PCR
- 7.2.3 Genomic variations of SARS-CoV-2 before and after CP transfusion
- 7.2.4 Transfer to ICU
- 7.2.5 Type and duration of respiratory support (and other ICU support including ECMO, CRRT) in ICU
- 7.2.6 Cardio-circulatory arrest (at any time)
- 7.2.7 ICU mortality and LOS
- 7.2.8 Hospital mortality and LOS
- 7.2.9 Ventilator-free days
- 7.2.10 In hospital mortality
- 7.2.11 Titer of other functions of antibodies, including antibody-dependent cell-mediated and complement-dependent cytotoxicity

7.3. Safety Endpoints:

- 7.3.1 Rapid deterioration of respiratory or clinical status on transfusion of SARS-CoV-2 convalescent plasma.
- 7.3.2 Cumulative incidence of serious adverse events during the study period: febrile non-hemolytic transfusion reaction, allergic transfusion reaction, transfusion related acute lung injury (TRALI), transfusion associated circulatory overload (TACO),

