PROTOCOL TITLE: Open, non-comparative pilot study to provide access to treatment with investigational convalescent plasma and measure antibody levels in patients hospitalized with COVID-19

transfusion related infection, hemolytic transfusion reaction or evidence of antibody dependent enhancement of infection (ADE).

8. Research Setting

The study will be conducted in the University of New Mexico Hospital. Patients admitted to the COVID-19 units including the emergency department, regular wards and intensive care units will be enrolled. Patients will be identified from the TriCore Laboratory testing result portal available to the research team or upon notification by providers in the participating institutions. Approval by the treating provider will be requested before patient enrollment and consent.

There is no external sponsor for this research. Immune assays and genomic studies will be performed utilizing existing resources within the [name] and [name] laboratories in the Center for Global Health.

SARS-CoV-2 neutralizing antibody titers will be measured using the focus reduction neutralization test (FRNT) in [name] Laboratory, Center for Global Health (CGH), UNMHSC. Neutralization assays will be conducted using methods already established in the [name] laboratory. Briefly, serial dilutions of plasma will be incubated with 50-100 pfu of SARS-CoV-2 at equal volumes for 1 hour and added to Vero E6 cells, followed by overlaying with agarose. Two days later cells will be fixed with 4% formaldehyde, stained with crystal violet, and plaques will be counted. Other functions of antibody, including antibody-dependent cell-mediated cytotoxicity and complement-dependent cytotoxicity, will be ascertained using established methods.

Virus sequencing will be performed in the laboratory of [name] in the Center for Global Health using the PCR-based NGS sequencing protocol described by the ARTIC Network <https://artic.network/ncov-2019>

9. Resources Available

9.1. Principal investigator and co-investigators are experienced Pulmonary, Critical Care, Infectious Disease ID Pharmacists, Virologist or Transfusion Medicine specialists with ample experience in conducting clinical trial and with the use of CP in previous clinical studies (GM):

- 9.1.1. [name], is a Pulmonary and Critical Care Medicine specialist and is the Chief of the Division of Pulmonary at UNMH
- 9.1.2. [name], is an Infectious Disease Attending and is the Chief of Infectious Diseases at UNMH.

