13.2. Data analysis will be limited to hospitalized subjects with respiratory symptoms and laboratory confirmation of SARS-CoV-2 infection by detection RNA in upper or lower respiratory samples (nasal or oral swabs or endotracheal fluid) or blood or by detection of NAb in serum. Subjects without laboratory-confirmed COVID 19 will be excluded from analysis.

Neutralizing antibody titers in the patient's first blood sample (day 0) will be compared by rank sum (Wilcoxon) test between patients who develop any of the secondary

PROTOCOL TITLE: Open, non-comparative pilot study to provide access to treatment with investigational convalescent plasma and measure antibody levels in patients hospitalized with COVID-19

clinical end-points and patients who do not develop these secondary endpoints. The same comparison will be performed to evaluate NAb titers with other parameters such as age ≥ 65 and < 65 , presence or absence of diabetes, or presence or absence hydroxychloroquine therapy. These analyses of day 0 NAb titers aim to characterize patient heterogeneity in NAb titers in relationship to patient demographic and clinical characteristics.

We will also analyze the association between NAb titers at day 0 with duration of viral shedding, duration of hospitalization and duration of intubation and other clinical parameters.

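### Endpoint 7.2.5 records respiratory support only in ICU and has no day-0 rule, although objective 1.2.4 sets no location limit and patients are enrolled on wards and in the emergency department

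*Combined protocol and SAP*

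**What the plan says.** All references are to the combined protocol and SAP.

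- **Endpoint (7.2.5):** "Type and duration of respiratory support (and other ICU support including ECMO, CRRT) in ICU".
- **Objective (1.2.4):** "Determine cumulative incidence of disease severity (transfer to ICU, type of respiratory support, LOS, and mortality". Nothing here confines respiratory support to one type of unit.
- **Setting (Section 8):** "Patients admitted to the COVID-19 units including the emergency department, regular wards and intensive care units will be enrolled".
- **Follow-up (Section 6):** patients "will be followed until hospital discharge or death", so time on a ward is inside follow-up.
- **Severity at entry (Section 4, exclusion 4):** "On ECMO or in refractory shock at entry". No other level of respiratory or organ support is excluded.
- **Use (13.2):** "Neutralizing antibody titers in the patient's first blood sample (day 0) will be compared by rank sum (Wilcoxon) test between patients who develop any of"; here the sentence goes on to name secondary clinical endpoints, with patients free of them as the other group. Later in 13.2, titres on post-transfusion days may also be related to secondary outcomes.
- **Neighbouring endpoints:** "Transfer to ICU" (7.2.4), cardio-circulatory arrest with no limit on when it occurs (7.2.6), hospital mortality (7.2.8 and 7.2.10) and "Ventilator-free days" (7.2.9).

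**The concern.** The objective and its endpoint do not cover the same events. The objective asks how many patients come to need each type of support. The endpoint answers only for time spent in ICU, in a study that recruits from three kinds of unit. A patient who goes from room air to high-flow oxygen on a ward and recovers there has had a respiratory event that 1.2.4 asks about and 7.2.5 does not record.

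The second problem is the starting point. Cumulative incidence, and the word *develop* in 13.2, both imply a change after some origin. A patient transfused in ICU may already be on the support that 7.2.5 records. Without a day-0 level, the reported frequency can mix how ill patients were on arrival with what happened to them afterwards.

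At stake are the descriptive severity results and any antibody association that uses respiratory support as the outcome. Section 19 argues that antibody given early should do more to prevent progression than to treat established severe disease. Progression from a milder entry state is what an ICU-only measure records least completely.

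**Working it through.** The plan states no figure for this endpoint, so there is none to reproduce. The check compares the text of the sections and then uses a small count to show direction.

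**Step 1. Which respiratory events reach a named endpoint?**

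| Event after transfusion | Captured by |
|---|---|
| Support of any type while in ICU | 7.2.5 |
| Worsening followed by a move to ICU | 7.2.4, then 7.2.5 |
| Mechanical ventilation in any unit | 7.2.9 (no ICU limit); 13.2 also mentions duration of intubation |
| Arrest in any unit | 7.2.6 |
| Death in any unit | 7.2.8, 7.2.10 |
| Sudden worsening during transfusion | 7.3.1 |
| Oxygen, high-flow or non-invasive support that starts and stays outside ICU | none named |

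The gap is the last row.

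**Step 2. Is support at entry separated from support that follows?** Exclusion 4 removes patients on ECMO or in refractory shock. A patient already ventilated, or on lesser support, in ICU can be enrolled. The visible text of Sections 7, 12 and 13 contains no rule that sets a day-0 support level, removes support already in place, or limits 7.2.5 to new or increased support. The wording of 1.2.4 and 13.2 suggests that new events were meant. The rule that would make this so is not there.

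**Step 3. Direction of the error.** The entry mix and escalation rates are not in the documents, so the counts below are assumptions chosen only to show direction. Take N = 30 (Section 5) and 5 patients newly supported in ICU. Let *b* be the number on support in ICU at entry and *w* the number newly supported only outside ICU. Each patient is classed simply as supported or not.

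- Endpoint read literally: (b + 5) / 30.
- New support in any unit among patients at risk: (5 + w) / (30 − b).

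| b | w | Literal 7.2.5 | New support among at risk |
|---|---|---|---|
| 0 | 6 | 5/30 = 17% | 11/30 = 37% |
| 6 | 0 | 11/30 = 37% | 5/24 = 21% |
| 6 | 6 | 11/30 = 37% | 11/24 = 46% |

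The literal figure can be too low or too high, and it does not show which. The literal result of 37% is compatible with 21% or 46% new support. Each patient classified differently moves a frequency by 1/30 = 3.3 percentage points.

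**The case against.** The strongest defence is that 7.2.5 may be a deliberate ICU measure, as 7.2.7 is, sitting among endpoints that catch the serious events elsewhere. Much of that stands. A reader might infer that a ward patient who worsens and dies there contributes nothing. That is true of 7.2.5 but not of the study, because the death counts under 7.2.8 and 7.2.10 and the other routes are listed above. What the defence does not cover is non-ventilator support given wholly outside ICU, which 1.2.4 includes.

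A reader might also infer that safety endpoint 7.3.1 is weakened for patients transfused on a ward. The documents do not support this. That endpoint is separate and has no location limit. It is monitored directly under 14.2, and Table 1 schedules four vital-sign checks around the infusion, together with symptom screening, physical assessment and adverse event monitoring.

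A third tempting reading is that the plan counts support at entry as an outcome. No section says so, and 1.2.4 and 13.2 lean the other way. What can be said is that the literal wording of 7.2.5 allows it and no visible rule prevents it.

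On use, the day-0 titre comparison in 13.2 is meant to describe heterogeneity between patients, not effects of plasma, so mixing in entry severity does less harm there. The post-transfusion associations give ICU transfer and hospital death as examples, not respiratory support. It is therefore not shown that every antibody association is biased, only that those using this outcome would inherit the ambiguity.

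Finally, Table 1 has a row for registering secondary clinical endpoints whose cell marks may have been lost when the PDF was read. Nothing here rests on missing collection times.

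**Conclusion.** The point holds, in a limited form. Endpoint 7.2.5 is narrower than objective 1.2.4, and non-ventilator respiratory support that begins and stays outside ICU has no named endpoint. In addition, patients already on support in ICU can enter, and no visible rule distinguishes that support from new or increased support, although the objective and the analysis speak of incidence and of developing endpoints.

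The size cannot be derived from the documents. It depends on how many of the 30 are enrolled outside ICU, how many of those escalate without moving, and how many arrive already supported. The illustration shows only that the error can go either way.

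The consequence is confined to secondary, exploratory outcomes, reported descriptively in a single-arm pilot, and to their antibody associations. Section 13 itself says that much of the secondary analysis is exploratory and that power is limited. The primary antibody analysis is unaffected. The change is worth making because it is cheap and because the reported severity frequencies are otherwise hard to interpret.

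**What to change.** 1. In 7.2.5, remove the ICU limit for respiratory support so that type and duration are recorded in any unit. The ECMO and CRRT part can stay as ICU support.
2. Record each patient's respiratory support level on day 0, before transfusion, from the chart, and report it as a baseline characteristic.
3. Define the outcome for 1.2.4 as the highest level reached from transfusion to discharge or death, taken from the whole stay. Recording only on days 1, 3, 7 and 14 would miss escalation that starts and resolves between visits.
4. Report new or increased support among patients at risk, with that denominator stated, separately from support present at entry. Report death alongside, so that a patient who dies without a change in support level is not read as stable.
5. Use the same definition wherever 13.2 groups patients by this endpoint.

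Items 1 and 2 belong together. If the ICU limit is dropped without a day-0 level, ward patients who arrive on oxygen would enter the count too.

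The cost is one reworded endpoint and a few more chart items per patient, with no added procedure. The at-risk denominator becomes smaller, because patients already ventilated at entry have little or no room to show an increase. The change is best made before enrolment, so that day-0 status is captured prospectively.

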PROTOCOL TITLE: Open, non-comparative pilot study to provide access to treatment with investigational convalescent plasma and measure antibody levels in patients hospitalized with COVID-19

- 12.1. Potential subjects will be identified by reviewing the registry of +SARSCoV2 RTPCR testing (at TRICORE laboratory) in hospitalized patients.
- 12.2. Eligibility of the potential study participants will be identified by their treating providers (Hospital Medicine and Intensive Care Unit). The treating providers will notify representatives of the research team. Members of the research team will verify the eligibility of the potential subjects and will obtain informed consent from them or their LAR.
- 12.3. Once the participant or their LAR gives their written informed consent, the research team will notify the treating provider so they can place the medical order for the investigational products. If LAR consented via phone, a copy of the consent form will be mailed to LAR.
- 12.4. The protocol specific activities are detailed in Table 1
- 12.5. Treatment

Subjects will receive the convalescent plasma.

Study drug: The investigational product is anti-SARS-CoV-2 convalescent plasma obtained from former patients identified as having recovered from COVID-19 and obtained by Vitalant from local and national donors following national blood donation guidelines. These donors will be cleared for blood donation like any other volunteer blood donor and samples will have been screened for transfusion-transmitted infections (e.g. HIV, HBV, HCV, WNV, HTLV-I/II, T. cruzi, ZIKV) both through the use of the uniform donor questionnaire and FDA mandated blood donor screening tests. This single-donor plasma product will have been collected using apheresis technology and in accordance with standard FDA and blood bank protocols.

A 1ml of aliquot of anti-SARS-CoV-2 plasma will be saved for NAb titer measurement by FRNT (as mention in section 8.) in the CGH laboratory and the total volume of plasma administration will be recorded.

 - 12.5.1. Study subjects will receive 1 unit (200mL) of SARS-CoV-2 convalescent plasma collected from a single donor who recovered from COVID-19.
 - 12.5.2. The anti-SARS-CoV-2 convalescent plasma will be in standard plasma blood unit bags, anticoagulated with a citrate-based anticoagulant (ACD-A, CP2D, et cetera), labeled with a specific ISBT product code, and stored in the UNM Blood Bank per FDA, AABB, and CAP protocols. Plasma transfusion will be administered over no more than four hours.

Table 1: Schedule of Events

PROTOCOL TITLE: Open, non-comparative pilot study to provide access to treatment with investigational convalescent plasma and measure antibody levels in patients hospitalized with COVID-19

Study period	Screen	Baseline	Transfusion	Follow-up			
Day	-1 to 0	0	0	1	3	7	14
Eligibility							
Informed consent	x						
Demographic and Medical history	x						
SARS-CoV-2 RT-PCR for eligibility	x						
Pregnancy test	x						
Type and screen	x						
Study Agent Administration							
Plasma Transfusion			x				
Study Procedures							
Vital signs	x	x	xxxx[1]	x	x	x	x
Physical assessment	x		x	x		x	
Symptom screen	x	x	x	x	x	x	x
Concomitant medications	x	x	x				

PROTOCOL TITLE: Open, non-comparative pilot study to provide access to treatment with investigational convalescent plasma and measure antibody levels in patients hospitalized with COVID-19

Adverse event monitoring		x	x	x	x	x	x	
Laboratory testing								
SARS-CoV-2 RT-PCR^[2] and Genomic analysis		x			x	x	x	
SARS-CoV-2 neutralizing antibody		x		x	x	x	x	
Secondary End point registration (clinical outcome)								

1. Vital sign testing: Immediately prior to infusion, 10-20 minutes after start of infusion, at completion of infusion and 30-60 minutes after the end of the infusion
2. Sampling can include nasopharyngeal, nasal or oropharyngeal swabs.

13. Data Analysis

13.1.1. We will determine whether there is a correlation between the NAb dose (in NAb units/kg body weight, where a unit is the reciprocal of the endpoint NAB titer in the CP multiplied by the volume in ml) and change or lack of change when comparing pre-treatment and day one NAb titers. We will also compare changes in pre- and post-treatment NAb titers based on NAb dosing calculated in units/BSA and units/calculated plasma volume to see if either measurement provides a better prediction of changes in NAb titers in recipients.

13.2. Data analysis will be limited to hospitalized subjects with respiratory symptoms and laboratory confirmation of SARS-CoV-2 infection by detection RNA in upper or lower respiratory samples (nasal or oral swabs or endotracheal fluid) or blood or by detection of NAb in serum. Subjects without laboratory-confirmed COVID 19 will be excluded from analysis.

Neutralizing antibody titers in the patient's first blood sample (day 0) will be compared by rank sum (Wilcoxon) test between patients who develop any of the secondary

PROTOCOL TITLE: Open, non-comparative pilot study to provide access to treatment with investigational convalescent plasma and measure antibody levels in patients hospitalized with COVID-19

clinical end-points and patients who do not develop these secondary endpoints. The same comparison will be performed to evaluate NAb titers with other parameters such as age ≥ 65 and < 65 , presence or absence of diabetes, or presence or absence hydroxychloroquine therapy. These analyses of day 0 NAb titers aim to characterize patient heterogeneity in NAb titers in relationship to patient demographic and clinical characteristics.

We will also analyze the association between NAb titers at day 0 with duration of viral shedding, duration of hospitalization and duration of intubation and other clinical parameters.

Our primary endpoint for statistical analysis is changes in NAb titers at day 1, 3, 7, and 14 from the entry level (day 0). Our primary hypothesis is that NAb titers will increase post-transfusion in positive correlation with transfused volume of convalescent plasma when adjusted for NAb titer in the convalescent plasma. We will use repeated measurements analysis of variance (ANOVA) or analysis of covariance (ANCOVA) when controlling for other factors (e.g. use of hydroxychloroquine) for initial exploration of the association with the transfusion volume of convalescent plasma. A more advanced approach is to use nonlinear regression models with random effects to characterize the trajectory of NAb titers over the course of 14 days. This latter approach can effectively characterize individual-specific trajectory in NAb titers in relation to convalescent plasma, and at the same time quantify between-patients variation, thereby improving statistical power. This mixed-effects nonlinear regression modeling approach is also capable of adjusting for other factors as appropriate (e.g. patient age). We will also conduct post-hoc analysis of change in NAb titers from day 0 to a specific day (day 1, 3, 7, or 14) post transfusion of convalescent plasma when appropriate. Better understanding and better characterization of the relationship between NAb titers and amount of convalescent plasma transfusion adjusted for NAb titer in the convalescent plasma will inform standardized dosage for future study.

In the absence of a comparison group, we will use descriptive statistics to report other parameters of interest (e.g. secondary outcomes), including the use of mean (SD), frequency (%) and their confidence interval. When appropriate, we will also report association between a parameter of interest and a factor of clinical relevance (e.g. duration of shading and underlying comorbidities, NAb titers at a specific post-transfusion day and underlying comorbidities, NAb titers at a specific post-transfusion day and secondary outcomes such as transfer to ICU or hospital death). This analysis will utilize odds ratio and Fisher's test for dichotomous variables, and Wilcoxon test a continuous variable.

We will conduct interim analysis after the first 10 patients complete the study. Based on the interim analysis results we may consider submitting a protocol amendment requesting adjustment our patient recruitment or CP dosing.

PROTOCOL TITLE: Open, non-comparative pilot study to provide access to treatment with investigational convalescent plasma and measure antibody levels in patients hospitalized with COVID-19

Given that we have a large number of clinical parameters of potential interest and a small sample of 30 patients, we do not have the statistical power or data depth for all analyses. The focus of our analysis is on the primary outcome and primary hypothesis. Much of the analyses of secondary outcomes are of the nature of exploration. We will adjust for multiplicity of comparisons (e.g. associations) using False Discovery Rate (FDR) in reporting our findings.

13.3. Sample size. A sample size determination is less plausible for this pilot study since we aim to establish the effect size of convalescent plasma transfusion on Nab titers.

However, we will conduct a post-hoc statistical power analysis to determine the actual power with the sample we obtain.

14. Provisions to Monitor the Data to Ensure the Safety of Subjects

14.1. A DSMB will be convened to include clinicians specializing in clinical trials, transfusion medicine and biostatisticians. The roster will be provided in a Modification for HRRC approval once the DSMB has been created.

14.2. The safety information that will be collected and monitored as follows: reports of rapid deterioration of respiratory or clinical status on transfusion of SARS-CoV-2 convalescent plasma and cumulative incidence of serious adverse events during the study period: febrile non-hemolytic transfusion reaction, allergic transfusion reaction, transfusion related acute lung injury (TRALI), transfusion associated circulatory overload (TACO), transfusion related infection, and hemolytic transfusion reaction.

14.3. Review of data after 10 participants have been enrolled.

14.4. Considering the novelty and rapidly changing situation of the COVID-19 pandemic, the investigators will review relevant publications that may help inform decisions related to the efficacy and safety of the investigational products.

14.5. The occurrence of any serious adverse event will be notified to the HRRC in accordance with GCP regulations. An analysis of all adverse events will be presented with the analysis of the first 10 patients enrolled and periodically thereafter.

14.6. The conditions that would trigger a suspension or termination of the research (i.e., stopping rules), are as follows:

a. If available published information convincingly reports non-efficacy or significant safety concerns with the use of SARS-CoV-2 convalescent plasma.

b. If an unexpectedly high incidence of serious adverse events judged to be related to SARS-CoV-2 convalescent plasma is detected in these critically ill COVID-19 patients during the trial in the clinical judgement of the investigators compared to that expected in similarly ill patients receiving normal donor plasma in the clinical judgement of the investigators.

PROTOCOL TITLE: Open, non-comparative pilot study to provide access to treatment with investigational convalescent plasma and measure antibody levels in patients hospitalized with COVID-19

- c. If there is an unanticipated safety signal, stopping the study will be considered.

14.7. Findings will be reported to the HRRC within 5 business days and to the FDA accordingly. A preliminary analysis of the study end points will be performed after 10 patients have been enrolled and end-points reached. The results will be presented to the HRRC and investigators.

15. Withdrawal of Subjects

15.1. Subjects will be withdrawn if the PI determines, in consultation with the treating clinician(s) that continuation in the study is not in the participant's best interest. Subjects may also withdraw (or be withdrawn by their LAR at their request at any time during their participation in the study by contacting a member of the study team.

15.2. If a patient develops a serious adverse event that may be probably or definitely related to the CP, during the infusion, that may trigger the discontinuation of the offending drug.

15.3. If a participant is withdrawn from the study, chart review will continue to be performed to track the participant's clinical outcomes.

15.4. Data and specimens collected before withdrawal will not be removed from the study.

16. Data Management/Confidentiality

16.1. Participants will be assigned a randomly generated study ID that will be linked to identifiers (MRN, DOB) in a linking table to be kept separate from the research data. Data and specimens will be labelled with the study ID only.

16.2. Only HRRC-approved members of the study team who have the appropriate training will have access to the data and identifiers.

16.3. Data will be entered into REDCap on a password-protected computer using a secure network.

16.4. Any hard copy records/data will be kept in a locked file cabinet in the locked office of a designated member of the study team

16.5. Once data collection is complete, data will be de-identified by destruction of the linking table. Study records will be kept for 6 years past study closure.

17. Data and Specimen Banking

Not Applicable

18. Risks to Subjects

PROTOCOL TITLE: Open, non-comparative pilot study to provide access to treatment with investigational convalescent plasma and measure antibody levels in patients hospitalized with COVID-19

18.1 Published data on convalescent antibody administration in SARS (Cheng 2005 and Yeh 2005) and SARS and MERS (Mair-Jenkins 2015), and preliminary data on convalescent plasma administration in COVID-19 (Shen 2020 and Duan 2020), also suggests that CP is safe and well tolerated.

18.2 One theoretical risk involves the phenomenon of antibody-mediated enhancement of infection (ADE). ADE can occur for several viral diseases and involves an enhancement of disease in the presence of certain antibodies. For coronaviruses, several mechanisms for ADE have been described and there is the theoretical concern that antibodies to one type of coronavirus could enhance infection to another viral strain (Casadevall, 2020). It may be possible to predict the risk of ADE of SARS-CoV-2 experimentally, as proposed for MERS. Since the proposed use of convalescent plasma in the COVID-19 epidemic would rely on preparations with high titers of neutralizing antibody against the same virus, SARS-CoV-2, ADE may be unlikely. The available evidence from the use of convalescent plasma in patients with SARS1 and MERS and anecdotal evidence of its use in patients with COVID-19 (Casadevall 2020), suggest it is safe. Nevertheless, caution and vigilance will be required in for any evidence of enhanced infection. Both COVID-19 and ADE may cause ARDS, and we recognize that this will be very difficult to attribute etiology in this small pilot study. None-the-less, we will pay particular attention to the incidence of ARDS in study subjects without comorbidities predicting risk of progression to severe disease, and we will closely follow any reports suggesting ADE that emerge from multicenter, placebo-controlled trials of CP, including two proposed CTSC-based RCTs for outpatient PrEP and outpatient treatment of early COVID-19 with CP, and we will forward any reports suggesting ADE to the IRB.

18.2 Another theoretical risk is that antibody administration to those infected by SARS-CoV-2 may avoid disease but modify the immune response such that those individuals mount attenuated immune responses, thereby leaving them vulnerable to subsequent re-infection. It will not be feasible to assess this risk in data collected in this hospital-based treatment study, but we will monitor the emerging scientific literature and report any concerning findings to the IRB.

18.3 There are risks associated with any transfusion of plasma including transmission of transfusion transmitted viruses (e.g. HIV, HBV, HCV, etc.), allergic transfusion reactions, anaphylaxis to transfusion, febrile transfusion reaction, transfusion related acute lung injury (TRALI), transfusion associated cardiac overload (TACO), and hemolysis should ABO incompatible plasma be administered. In order to minimize the risks of disease transmission, donors will fulfill donor requirements for blood donation with the exception of recent illness, in this case COVID-19 infection.

18.4 Venipuncture can cause bruising, bleeding and mild discomfort. It is infrequently associated with infection. To minimize the risk of phlebotomy, only adequately trained

PROTOCOL TITLE: Open, non-comparative pilot study to provide access to treatment with investigational convalescent plasma and measure antibody levels in patients hospitalized with COVID-19

study personnel or hospital personnel will draw blood. Blood volumes to be obtained fall within OHRP guidelines for minimal risk studies. Alternative procedures are not feasible.

18.5 Breach of confidentiality from data obtained during the enrollment interview or clinical charts. Subject confidentiality will be maintained by the following methods: All records will be kept in a locked file. All computer entry and networking will be performed with coded numbers only. Clinical information will not be released without written permission from the subject. Access to identified, source records will be limited to the local site principal investigator and study personnel.

18.6. 1.1.1. Mild to discomfort from obtaining NP. Nasal swabs can be performed without discomfort or risk. To minimize discomfort from obtaining nasal or NP swabs, these will be obtained by trained medical personnel, and subjects who cannot tolerate NP swabs will only have nasal swabs obtained.

19. Potential Benefits to Subjects

A key potential benefit is treatment for established infection. Convalescent plasma would be administered to those with clinical disease in an effort to reduce their symptoms and mortality. Based on the historical experience with antibody administration, it can be anticipated that *antibody administration relatively early in the course of disease would be more effective in preventing disease progression than in the treatment of established severe disease.*

Given that historical and current anecdotal data on use of convalescent plasma suggest it is safe in coronavirus infection, the high mortality of COVID-19, particularly in elderly and vulnerable persons, suggests that the benefits of its use in those at high risk for or with early disease outweigh the risks. However, for all cases where convalescent plasma administration is considered, a risk-benefit assessment must be conducted to assess individual variables.

20. Recruitment Methods

Members of the research team will review the list of admitted or hospitalized patients with a positive SARS-CoV-2 test. Alternatively, treating providers may also notify the research team of the admission of SARS-CoV-2 patients or the positive result of a suspected COVID-19 patient.

21. Provisions to Protect the Privacy Interests of Subjects

- 21.1.** Only members of the research team will access trial related documents.
- 21.2.** All study procedures will be conducted in the participant's room or other private area of the hospital.

22. Economic Burden to Subjects

PROTOCOL TITLE: Open, non-comparative pilot study to provide access to treatment with investigational convalescent plasma and measure antibody levels in patients hospitalized with COVID-19

- 22.1. The study is responsible for the cost of any research-related procedures. The participant and/or third party payer is responsible for any standard of care procedures.
- 22.2. Investigators do not anticipate any additional costs.

23. Compensation

No compensation will be given to study participants.

24. Compensation for Research-Related Injury

The University of New Mexico does not have funds set aside to pay for the cost of any care or treatment that might be necessary or for any wages lost as a result of participating in this study. Medical costs to care and treatment of study related harm will be billed to the participant and/or third party payer.

25. Consent Process

